4.4. Stopping Rules for the Study

A conditional power approach will be used in case the IDMC considers an ET of the study due to poor efficacy, as applicable. Full details of this approach will be depicted in the IDMC charter and the statistical analysis plan. During the conduct of the study, all safety data will be reviewed as they are reported from the investigational centers to identify safety concerns.

The study may be terminated by the sponsor for any reason at any time. For example, the sponsor should terminate the study in the event of:

- new toxicological or pharmacological findings or safety issues that invalidate the earlier positive benefit-risk assessment
- discontinuation of the development of the IMP

If the whole study or arms of the study will be stopped, the patients who are terminated early will be followed according to Withdrawal Criteria and Procedures for the Patient (Section [5.4](#)).

4.5. Schedule of Study Procedures and Assessments

Study procedures and assessments with their time points are presented in [Table 1](#) (Period 1) and [Table 2](#) (Period 2). Detailed descriptions of each method of procedures and assessments are provided in Section [7](#) (efficacy assessments), Section [8](#) (safety assessments), and Section [9](#) (pharmacokinetic and other assessments). Study procedures and assessments by visit are listed in [Appendix B](#).

5. SELECTION AND WITHDRAWAL OF PATIENTS

Prospective waivers (exceptions) from study inclusion and exclusion criteria to allow patients to be randomized are not granted by Teva ([Appendix C](#)).

5.1. Patient Inclusion Criteria

Patients may be randomized in this study only if they meet all of the following criteria:

- a. [Revision 1] The patient is a male or female of any ethnic origin, 18 to 64 years of age, inclusive, at the time of screening.
- b. [Revision 1] The patient is capable of providing signed informed consent. Patients will be asked to consent to share their information with a vendor that will verify that they are not currently participating or have not recently participated in another clinical study, unless prohibited by local requirements.
[REDACTED]
[REDACTED]
[REDACTED]
[REDACTED]
- c. The patient has a current confirmed diagnosis of schizophrenia according to the DSM-5, for >1 year. Diagnosis must be reconfirmed by the SCID-5-CT.
- d. The patient has a total PANSS score between 80 and 120, inclusive, at screening and baseline (prior to randomization) with a score ≥ 4 on at least 2 of the following 4 items of the PANSS positive subscale: hallucinatory behavior, delusions, conceptual disorganization, or suspiciousness/persecution.
- e. The patient has exacerbation of schizophrenia that started ≤ 8 weeks prior to screening and would benefit from psychiatric hospitalization or continued hospitalization for symptoms of schizophrenia.
- f. The patient has a CGI-S score of ≥ 4 (moderately ill) at screening and baseline (prior to randomization).
- g. Patients who have received an antipsychotic treatment (other than clozapine) in the past year must have been responsive based on the investigator's judgment (and based on discussions with family members, caregivers, or healthcare professionals, as applicable).
- h. [Revision 1] The patient has an identified responsible person (referred to as the caregiver) who has agreed to provide information about the patient's location, condition, and overall status during outpatient portions of the study during Period 1. The site personnel must identify the caregiver at the screening visit and consider the caregiver a reliable contact person. The caregiver must have regular contact with the patient (defined as direct contact not fewer than 3 times per week), with the expectation that this frequency of contact would continue throughout the outpatient portion of Period 1 (it is also advised during the rest of the study, including Period 2 and the FU period). This regular contact with the patient is not mandatory during the

hospitalization period of Period 1. The patient's caregiver will be asked to sign a caregiver ICF during the screening period.

- i. Body mass index between 18.0 and 40.0 kg/m², inclusive, at the time of screening.
- j. Women may be included only if they have a negative beta-human chorionic gonadotropin (β-HCG) test at screening and baseline (if a borderline result is obtained on a urine test, a serum test should be performed and a negative result obtained) or are sterile (documented hysterectomy, bilateral oophorectomy, or bilateral salpingectomy or congenitally sterile) or postmenopausal ([Appendix E](#)).
- k. Women of childbearing potential must agree not to try to become pregnant, and, unless they have exclusively same-sex partners, must agree to use a highly effective method of contraception prior to the first administration of IMP, and agree to continue the use of this method for the duration of the study, and for 70 days after the last dose of IMP. Highly effective methods of contraception include the following:
 - Combined estrogen and progestogen hormonal contraception (oral, intravaginal, transdermal) associated with inhibition of ovulation; these should be initiated at the screening visit before the first dose of IMP.
 - Progestogen-only hormonal contraception (oral, injectable, implantable) associated with inhibition of ovulation; these should be initiated at the screening visit before the first dose of IMP.
 - Intrauterine device and intrauterine hormone-releasing system; these need to be in place at least 2 months before screening.
 - Bilateral tubal occlusion.
 - Vasectomized partner, provided that he is the sole sexual partner and has received medical assessment of the surgical process.
 - Sexual abstinence is **only** considered a highly effective method if defined as refraining from heterosexual intercourse in the defined period. The reliability of sexual abstinence needs to be evaluated in relation to the duration of the clinical study and the preferred and usual lifestyle of the patient.
- l. The patient, if an adult male, is surgically sterile, or, if capable of producing offspring, has exclusively same-sex partners or is currently using an approved method of birth control and agrees to the continued use of this method for the duration of the study (and for 70 days after the last dose of IMP). Male patients with sex partners who are women of childbearing potential must use condoms even if surgically sterile. In addition, male patients may not donate sperm for the duration of the study and for 70 days after the last dose of IMP.
- m. The patient is able to understand the nature of the study and follow protocol requirements, including the prescribed dosage regimens (oral and sc administration), non-use of prohibited concomitant medications, and hospitalization for at least 4 weeks at the clinical site; can read and understand the written word in order to complete patient-reported outcomes measures by themselves; and can be reliably rated on assessment scales.

- n. The patient must be willing and able to comply with study restrictions and to remain at the investigational center for the required duration during the study period (including hospitalization for at least 4 weeks at the clinical site) and must be willing to return to the investigational center for further visits, as applicable, and for the FU procedures and assessments as specified in this protocol.
- o. The patient has a stable place of residence for approximately 3 months before screening, and changes in residence are not anticipated over the course of study participation.
- p. The patient is in adequate health as determined by medical and psychiatric history, medical examination, electrocardiogram (ECG), serum chemistry, hematology, coagulation urinalysis, and serology.

5.2. Patient Exclusion Criteria

Patients will not be randomized in this study if they meet any of the following criteria:

- a. The patient has a current clinically significant DSM-5 diagnosis other than schizophrenia (has a primary current diagnosis other than schizophrenia or a comorbid diagnosis that is primarily responsible for the current symptoms and functional impairment).
- b. The patient has a known history of the following: (a) borderline personality disorder, antisocial personality disorder, or bipolar disorder; (b) traumatic brain injury causing ongoing cognitive difficulties, Alzheimer’s disease, or another form of dementia, or any chronic organic disease of the central nervous system; and (c) intellectual disability of a severity that would impact ability to participate in the study.
- c. The patient has an improvement (reduction) in the total PANSS score of $\geq 20\%$ between screening and day 1 (baseline [randomization] visit).
- d. The patient was hospitalized for >14 days (with the exception of social or administrative hospitalization) in the current exacerbation episode prior to screening.
- e. The patient has a significant risk of violent behavior based on the patient’s medical history or investigator’s judgment.
- f. The patient has a significant risk of committing suicide based on the patient’s medical history or C-SSRS, and the investigator’s judgment.

Patients with a C-SSRS positive response to suicidal ideation items 3, 4, or 5 and/or positive suicidal behavior response in the past 6 months are not eligible.

- g. The patient meets criteria for moderate to severe substance use disorder (based on DSM-5 criteria) within the past 6 months, such as chronic alcohol abuse or drug abuse (excluding those related to caffeine or nicotine). If, per the investigator’s judgment, a patient does not meet the criteria for substance use disorder, a positive result on the urine drug test is not exclusionary. Patients’ eligibility in such case of positive result, without medical explanation, will be determined by the investigator based on the patient’s background, history of substance use, and the investigator’s

discussions with family members, caregivers, or healthcare professionals, as applicable.

- h. The patient is currently using an LAI antipsychotic or is still under the coverage period of the specific LAI at time of screening.
- i. The patient has taken clozapine or has received electroconvulsive therapy within the last 12 months prior to screening.
- j. The patient is currently receiving daily oral olanzapine at a dose >20 mg/day.
- k. The patient has current or a history of known hypersensitivity to olanzapine or any of the excipients of TV-44749 or the oral formulation of olanzapine.
- l. The patient has treatment-resistant schizophrenia according to medical and psychiatric history, as judged by the investigator or documented failure of 2 or more antipsychotic medications (administered at the maximum tolerated dose for at least 6 weeks each). Participants who have responded to antipsychotics only when paired with clozapine are considered treatment resistant.
- m. The patient has had a significant sedation or delirium after antipsychotic treatment according to medical and psychiatric history and as judged by the investigator or suffered from delirium due to a medical condition.
- n. [Revision 1] The patient has any medical or psychiatric condition that, in the opinion of the investigator, could jeopardize study participant's safety (including in the context of local oral olanzapine label) or would compromise the patient's ability to participate in this study.
- o. The patient has known risk factors for undiagnosed/instable arrhythmia, congenital long QT, hypokalemia, hypomagnesemia, or autonomic failure (mostly with clinically significant orthostatic hypotension).
- p. The patient has any clinically significant uncontrolled medical condition (treated or untreated).
- q. Any disorder that may interfere with absorption, metabolism, or elimination of olanzapine
- r. The patient has a non-fasting glucose level of ≥200 mg/dL at screening.
- s. The patient had a change in their diabetes treatment within 4 weeks before the first injection of the IMP.
- t. The patient has serum triglycerides levels of ≥500 mg/dL.
- u. The patient has low-density lipoprotein levels of ≥190 mg/dL.
- v. The patient has a history of ketoacidosis or hyperosmolar coma.
- w. [Revision 1] The patient has alanine aminotransferase (ALT)/serum glutamic pyruvic transaminase values $\geq2 \times$ the upper limit of normal (ULN) of the performing laboratory, and aspartate aminotransferase (AST)/serum glutamic oxaloacetic transaminase values $\geq2 \times$ ULN, and total bilirubin values $\geq1.5 \times$ ULN at screening.

Isolated parameters for exclusion are as follows:

- ALT or AST $>5 \times$ ULN
- ALT or AST $>3 \times$ ULN, and in addition either total bilirubin level $>2 \times$ ULN or international normalized ratio >1.5 (if elevation of international normalized ratio is not caused by anticoagulants)
- ALT or AST $>3 \times$ ULN with the appearance of fatigue, nausea, vomiting, right upper quadrant pain or tenderness, fever, rash, and/or eosinophilia ($>5\%$)
 - x. The patient has a neutrophil count of $<1200/\text{mm}^3$.
 - y. The patient has platelet count $\leq 75 \times 10^3 \mu\text{L}$.
 - z. The patient has serum creatinine $>2.5 \text{ mg/dL}$.
- aa. The patient has a positive serology for human immunodeficiency virus (HIV)-1, HIV-2, hepatitis B surface antigen, and/or hepatitis C. If serology is positive for hepatitis C but the ribonucleic acid (RNA) test is negative, and the patient has no history of liver disease or symptoms of active liver disease, enrollment will be allowed based on clinical judgment.
- bb. The patient is a pregnant or lactating woman or plans to become pregnant during the study.
- cc. The patient has previously participated in this study (except for rescreening).
- dd. The patient is or has been using or consuming the medications prohibited in this protocol.
- ee. The patient used an investigational drug (new chemical entity) or a medical device in a clinical study within 30 days or 5 half-lives (whichever is longer), or, in case of a biologic investigational drug, within 3 months or 5 half-lives (whichever is longer) prior to the first TV-44749 administration.
- ff. The patient has donated or received any blood, plasma, or platelet transfusions within 30 days prior to the study or have planned donations during the study period or 6 months following the last dose of IMP administration.
- gg. The patient has a pending court appearance that may result in incarceration.

5.3. Eligibility Criteria for Period 2

In order to enter Period 2, the patient should meet the following eligibility criteria:

1. Patient has completed Period 1.
2. Patient is considered sufficiently clinically stable per the investigator's judgment.
3. Patient is an outpatient (ie, met RDQ criteria and was discharged prior to Period 2).

Note: Patients who do not meet RDQ criteria, but in the opinion of the investigator show sufficient clinical stabilization for transition to Period 2 and may benefit from continuation of participation in the study, may continue to Period 2 as inpatients for up to an additional 8 weeks. For such patients, RDQ can be assessed periodically according to investigator discretion; if RDQ criteria are not met by the end of the additional 8-week

hospitalization period (week 16), then the patient will be discontinued from study treatment and will be asked to complete ET and FU visits.

5.4. Withdrawal Criteria and Assessments/Procedures for the Patient

Patients are expected to participate in the study for its entire duration and perform the scheduled visits and procedures. Each patient is free to withdraw from the study or discontinue treatment with IMP at any time, without prejudice to their continued care, but every effort should be undertaken to determine the reason for discontinuation.

Patients must discontinue treatment with IMP and/or withdraw from the study if any of the following events occur:

1. Patient withdraws consent or requests discontinuation from the IMP and/or withdrawal from the study for any reason.
2. Patient develops an illness that would interfere with his/her continued participation.
3. Patient is noncompliant with the study procedures and assessments or administration of IMPs in the opinion of the investigator.
4. Patient takes prohibited concomitant medications as defined in this protocol (final decision to withdraw the patient will be on a case-by-case basis per sponsor discretion).
5. A female patient has a confirmation of pregnancy during the study from a positive pregnancy test.
6. The sponsor requests withdrawal of the patient.
7. Patient experiences an adverse event or other medical condition which indicates to the investigator that continued participation is not in the best interest of the patient.

Additionally, patients who meet the following study-specific criteria will be early terminated (ie, discontinued from further treatment with IMP and encouraged to complete the EOT and FU visits):

1. Patient is diagnosed with a clinically significant DSM-5 disorder other than schizophrenia.
2. A patient demonstrates a significant clinical deterioration that cannot be managed with permitted rescue medication as judged by the investigator based on any relevant history or observation made by the investigative site, and/ or requires other antipsychotic treatment apart from TV-44749. Hospitalization due to deterioration of schizophrenia that does not require other antipsychotic treatment will not be a withdrawal criterion unless determined as such by the investigator.
3. A patient experiences 3 events of pus-containing lesions (abscess, infection, or inflammation) at the site of injection requiring intervention/systemic treatment following 3 separate IMP injections.

Patients should be treated with standard of care after withdrawal from or termination of the study as appropriate.

Investigators should attempt to obtain information on patients in case of withdrawal from the study or discontinuation from the IMP. Results of any evaluations and observations, together with a narrative describing the reason(s) for withdrawal from the study or discontinuation from the IMP, must be recorded in the source documents. The CRF must document the primary reason for withdrawal from the study or discontinuation from the IMP.

See [Appendix F](#) for information regarding how the study will define and address lost to follow-up patients to help limit the amount and impact of missing data.

If the reason for withdrawal from the study or discontinuation from the IMP is an adverse event and/or clinically significant abnormal laboratory test result, monitoring will be continued as applicable (eg, until the event has resolved or stabilized, until the patient is referred to the care of a health care professional, or until a determination of a cause unrelated to the IMP or study procedure is made). The specific event or test result (including repeated test results, as applicable) must be recorded both on the source documentation and in the CRF; both the adverse events page and the relevant page of the CRF will be completed at that time.

The patient will be monitored as applicable (eg, until the event has resolved or stabilized, until the patient is referred to the care of a health care professional, or until a determination of a cause unrelated to the test IMP or study procedure is made). The investigator must inform the MM or other applicable study contact person as soon as possible of each patient who is being considered for withdrawal due to adverse events. Additional reports must be provided when requested.

If a patient is withdrawn from the study and/or discontinues the IMP for multiple reasons that include also adverse events, the relevant page of the CRF should indicate that the withdrawal was related to an adverse event. An exception to this requirement will be the occurrence of an adverse event that in the opinion of the investigator is not severe enough to warrant discontinuation but that requires the use of a prohibited medication, thereby requiring discontinuation of the patient. In such a case, the reason for discontinuation would be “need to take a prohibited medication,” not the adverse event.

In the case of patients lost to follow-up, attempts to contact the patient must be made and documented in the patient’s medical records and transcribed to the CRF.

Randomized patients who meet 1 or more of the study discontinuation or withdrawal criteria should be invited to perform the ET visit as soon as possible. An EOT visit will be conducted at 4 weeks after the last dose of IMP, and a FU visit for safety evaluation will be conducted at 8 weeks after the last dose of IMP. In case the ET visit is conducted during the time window of the EOT visit, the ET and EOT visits may be conducted on the same day (ie, the visits will be combined, and all assessments listed in the Study Procedures and Assessments tables [[Table 1](#) or [Table 2](#)] for the ET and EOT visits must be performed). Patients who discontinue study treatment should be encouraged to complete the remaining visits until completion of the study (ie, ET, EOT, and FU visits).

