In addition, any use of prohibited antipsychotics after early termination is not considered an ICE. Prior antipsychotic medications without a defined end-date are not deemed as ICE of "prohibited concomitant antipsychotic medication" since these cases occur before randomization and initiation of treatment.

Table 1: Classification of Intercurrent Events

Intercurrent Event	Strategy	Handling of Intercurrent Events

 • Early discontinuation of treatment due to: 
 ◦ lack of efficacy ◦ disease progression • Prohibited antipsychotic (with the exception above) 	Hypothetical	Measurements after ICE will be removed and replaced with imputed data using reference-based (CIR) imputation (assuming MNAR)

 • Early discontinuation of treatment due to other reasons (including due to adverse event) 	Hypothetical	Measurements after ICE will be removed and replaced with imputed data based on randomized treatment group (assuming MAR)

 • Allowed concomitant medications • Adverse event that did not lead to treatment discontinuation • Use of prohibited medications that are not antipsychotic • Short term use of prohibited antipsychotic (see meeting the definition above) • Injection site reaction • Out of window safety assessments 	Treatment policy	Measurements after ICE will be included in the primary analysis

ICE=intercurrent event; MAR=missing at random; MNAR=missing not at random; CIR = copy increments in reference

Any data collected after the intercurrent event (ICE) of taking prohibited antipsychotic medications (except as described above) or withdrawal from randomized treatment due to insufficient clinical response (i.e., lack of efficacy) will be treated in the analysis as MNAR. An ICE of early discontinuation for other reasons will be treated in the analysis as if the patient fully complied and completed the study (i.e., assuming missing at random [MAR]); see Table 1 for further details on the classification and handling of ICEs. This complies with the hypothetical approach.

For ICEs that were not foreseen at the time of writing the protocol and that require the use of the hypothetical strategy, classification as MAR/MNAR and revisiting this classification will be done in a blinded manner on a case-by-case basis prior to database lock for efficacy and will be

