APPENDIX B. MULTIPLE IMPUTATION DETAILS**Primary Analysis****Data preparation**

Intercurrent events (ICEs) are defined in [Table 1](#) (Section 1.2.1). Visits where an ICE occurred will be labelled with the appropriate ICE type:

USUBJID	TRT01P	AVISITN	AVISIT	ADY	AVAL	CNSRDT	EVNTDESC
██████████	Placebo	4		Visit 4/ Week 1		██████████	
██████████	Placebo	5	██████████	Visit 5/ Week 2	2	██████████	Prohibited antipsychotic
██████████	Placebo	6		Visit 6/ Week 3	2	██████████	Prohibited antipsychotic
██████████	Placebo	7		Visit 7/ Week 4	2	██████████	Prohibited antipsychotic
██████████	Placebo	8		Visit 8/ Week 5	2	██████████	Prohibited antipsychotic
██████████	Placebo	9		Visit 9/ Week 6	2	██████████	Prohibited antipsychotic
██████████	Placebo	10		Visit 10/ Week 7	2	██████████	Prohibited antipsychotic
██████████	Placebo	11		Visit 11/ Week 8	2	██████████	Prohibited antipsychotic

The classification of intercurrent events (ICEs) will be performed as follows:

Event	CNSR	EVNTDESC
Early termination from randomized treatment due to "Lack of Efficacy" or an Adverse Event of "Exacerbation of schizophrenia"	1	ET due to lack of efficacy
An oral antipsychotic use was documented in the CRF (Concomitant Medication or Protocol Deviations) and reviewed in a blinded manner in the statistical data review meeting and does not meet the conditions in Section 1.2.1	2	Prohibited antipsychotic
Early termination from randomized treatment due to other reasons	3	ET due to other reasons

Multiple Imputation Method

[figure not shown]
Parameter Estimation Model

Imputation of ICE data under MAR

Imputation of ICE data under MNAR

[figure not shown]

Analysis model

[figure not shown]
Tipping Point Analysis (Two dimensional)

Tipping Point Analysis (One dimensional)

[figure not shown]
[figure not shown]
[figure not shown]
[figure not shown]
[figure not shown]
The above process will be repeated, but the delta value for the placebo group will be held at zero. The range of delta values and increments may be adjusted post hoc depending on the observed treatment effect in order to most effectively characterize the “tipping point”.

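### Some active-arm treatment failures get active-arm instead of placebo increments, because adverse events take precedence in the recorded withdrawal reason and SAP Appendix B code 1 is narrower than Table 1

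*Protocol*

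**What the plan says.** **Recording.** Protocol 5.4 asks for one reason: "The CRF must document the primary reason for withdrawal from the study or discontinuation from the IMP". When a patient leaves for several reasons and one of them is an adverse event, "the relevant page of the CRF should indicate that the withdrawal was related to an adverse event". There is one carve-out, which begins "An exception to this requirement will be the occurrence of an adverse event that in the opinion of the investigator is not severe enough": if such an event calls for a prohibited medication, the recorded reason is the need for that medication and not the event. The same section requires a narrative of the reason or reasons in the source documents.

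**Imputation.** SAP 1.2.1, Table 1, has two hypothetical-strategy classes:
- For lack of efficacy, disease progression, and prohibited antipsychotic use beyond the short-term allowance: "Measurements after ICE will be removed and replaced with imputed data using reference-based (CIR) imputation (assuming MNAR".
- For "Early discontinuation of treatment due to other reasons (including due to adverse event": "Measurements after ICE will be removed and replaced with imputed data based on randomized treatment group (assuming MAR".

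**Coding.** SAP Appendix B turns this into codes. Code 1 is "Early termination from randomized treatment due to 'Lack of Efficacy' or an Adverse Event of 'Exacerbation of schizophrenia". Code 2 is prohibited antipsychotic use. Code 3 is every other early termination. Disease progression, which Table 1 names, does not appear in code 1.

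**Intent.** SAP 1.2.1 and 6.2.3 say that patients who stop for lack of efficacy are to follow the placebo group's course from that point, and 6.2.3 reserves MAR for reasons other than lack of efficacy.

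**The concern.** Letting an adverse event take precedence over other reasons is a sensible safety-reporting convention. Here the recorded reason also appears to decide the imputation, so the convention can displace the estimand's own rule for treatment failure.

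The overlap is built into the protocol. Section 8.1.1 counts marked worsening of the study disease as an adverse event, and 5.4 lists clinical deterioration as a ground for early termination. A patient who is failing treatment may therefore carry an adverse event, either the worsening itself under some term or an unrelated side effect. Appendix B rescues only one term, and does not say whether it means the investigator's wording or the coded term.

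At stake is a one-directional error in the primary comparison of each dose with placebo.

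**Working it through.** **1. Trace the cases through the text.**

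| Why the patient stops | Recorded reason under Protocol 5.4 | Class intended by SAP 1.2.1 | Appendix B read literally |
|---|---|---|---|
| Lack of efficacy only | Lack of efficacy | CIR | Code 1, CIR |
| Adverse event termed exacerbation of schizophrenia | Adverse event | CIR | Code 1, CIR |
| Lack of efficacy plus, say, sedation | Adverse event | CIR for the lack-of-efficacy part; no tie-break written | Code 3, MAR |
| Worsening of schizophrenia under another adverse-event term | Adverse event | CIR (disease progression) | Code 3, MAR |

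The last two rows are the problem.

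**2. Error per misclassified patient.** Let d(k) be the mean benefit over placebo at Week k. After stopping at Week k, MAR adds the active arm's later mean increment and CIR adds placebo's. Both also carry forward the patient's own deviation from the arm mean, and that term cancels if the two use the same fitted model (the model details are redacted). So

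MAR minus CIR, as excess benefit = d(8) − d(k).

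In the placebo arm the reference is the patient's own arm, so the gap is 0.

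**3. Inputs.** The plan gives no figure for this effect, and the effect size, SD and early-termination rate are redacted. Three assumed scenarios for stopping at Weeks 2 to 4:

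| Assumption | d(8) − d(k), points |
|---|---|
| A. d = 3.5, 5.0, 6.0 at Weeks 2, 3, 4; d(8) = 9.0 | 5.5, 4.0, 3.0 |
| B. d(k) = 8(1 − e^(−k/3))/(1 − e^(−8/3)) | 3.82, 2.57, 1.67 |
| C. d(8) = 8; 25%, 50%, 75% accrues after stopping | 2.0, 4.0, 6.0 |

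**4. Shift in an active arm's Week 8 mean** = share of the arm misclassified × gap.

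| | 2% of arm | 8% of arm |
|---|---|---|
| A | 0.06 to 0.11 | 0.24 to 0.44 |
| B | 0.03 to 0.08 | 0.13 to 0.31 |
| C | 0.04 to 0.12 | 0.16 to 0.48 |

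The overall range is 0.03 to 0.48 points. The top end is 0.48/8 = 6% of the assumed effect.

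**5. Is 2 to 8% plausible?** If 640 was obtained by inflating 440 completers for early termination, the implied rate is 1 − 440/640 = 31.25%. With 160 per arm that is 50 early terminations. Two percent of an arm is 3.2 patients, or 6.4% of them; 8% is 12.8 patients, or 25.6%. The upper end therefore needs about a quarter of an arm's early terminations to be misclassified.

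**6. What MAR gives these patients.** A simulation used trajectory B with a placebo change of −10 at Week 8, SD rising from 8 to 18, correlation 0.9 between adjacent weeks, and stopping when the score was more than 5 points worse than baseline. Patients who stopped at Weeks 2, 3 and 4 had mean changes of +9.0, +9.5 and +10.2. Imputed Week 8 changes were +0.7, +3.3 and +5.5 under MAR, and +4.5, +5.9 and +7.2 under CIR. Patients who stayed averaged about −19.

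**The case against.** **The link from recorded reason to code is inferred.** Appendix B's first row does not mention the CRF, and SAP 6.2.3 limits MAR to reasons other than lack of efficacy, so a mixed case does not clearly belong there. This stands in part: the link is a strong inference, not an explicit statement. It is strong because the exception in 5.4 shows that the rule sets the reason field, and a program needs a recorded reason to assign a code.

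**Blinded review could put such cases right.** SAP 1.2.1 and 5.7 provide for it, and the narrative will exist. But neither document gives a rule for mixed reasons, and the review is directed to Table 1, which sends adverse-event withdrawals to MAR.

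**Robustness is examined elsewhere.** The tipping-point analysis varies the active and placebo offsets independently, and the treatment-policy analysis does not use this classification. Both are useful, but neither identifies these patients or corrects the primary estimate. Sensitivity analysis #1 sets all events to MAR and so moves the same way as the error.

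**Stronger readings that a reader might infer:**
- That every mixed-reason withdrawal is recorded as an adverse event. The rule covers only reasons that include one, and has the prohibited-medication exception.
- That every adverse-event withdrawal goes to MAR. Appendix B moves exacerbation of schizophrenia to code 1, and qualifying prohibited antipsychotic use has its own code.
- That these patients are imputed as if they had kept responding. MAR conditions on their own poor scores. In the simulation they end well short of those who stayed, and only the later increments are too favourable.

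**Conclusion.** The point holds in this form: taken literally, Protocol 5.4 and SAP Appendix B together send some active-arm treatment failures to MAR where the primary estimand calls for placebo increments. The error can only favour TV-44749, provided drug benefit is still accruing when the patient stops and that MAR and CIR share one imputation model, so that they coincide under placebo.

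The likely overstatement is small, about 0.03 to 0.5 PANSS points per comparison. That rests wholly on assumed effects of 8 to 9 points, assumed time courses, and 2 to 8% of an arm affected. A reader might infer that the primary result is in jeopardy; nothing in the documents supports that. It is still worth correcting, because Appendix B does not fully carry out Table 1, the gap runs in the sponsor's favour, and no planned step closes it.

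**What to change.** In SAP Appendix B:
1. Align code 1 with Table 1 by adding disease progression, and worsening of schizophrenia under any adverse-event term.
2. State that when lack of efficacy or worsening is a documented contributing reason for stopping, the event is code 1 even if the CRF reason is adverse event.
3. Apply both rules at the planned blinded data review, using the withdrawal narrative that Protocol 5.4 already requires, and record each decision in the minutes.

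Leave the CRF coding as it is for the safety tables. An optional sensitivity analysis with all adverse-event withdrawals under CIR would show how far the classification matters.

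The cost is SAP wording, which SAP 2.6.2 allows before the first database lock, and a blinded reading of the adverse-event withdrawals. The downside is that a few patients who left mainly for toxicity will receive CIR, so the estimate becomes slightly more conservative.
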